**Protocol title**: Effect of a nutrition education and physical activity intervention on Metabolic Syndrome among females of reproductive age in Wakiso district, central Uganda: an individually randomized parallel-group trial

## LIST OF ABBREVIATIONS AND ACRONYMS

ATP III	National Cholesterol Education Program Adult Treatment Panel III	
BMI	Body Mass Index	
CHD	Coronary Heart Disease	
CVD	Cardiovascular disease	
DBP	Diastolic blood pressure	
FBG	Fasting blood glucose	
HDL	High-Density Lipoprotein Cholesterol	
IPAQ	Physical Activity Questionnaire	
LDL	Low-Density Lipoprotein Cholesterol	
MetS	Metabolic syndrome	
SBP	Systolic blood pressure	
T2DM	Type 2 Diabetes Mellitus	
TG	Triglycerides	
WHO	World Health Organization	

#### **OPERATIONAL DEFINITIONS**

**Cardiovascular diseases:** These diseases include coronary heart disease, cerebro-vascular disease, raised blood pressure, peripheral artery disease, rheumatic heart disease and congenital heart disease.

**Metabolic:** This refers to biochemical processes involved in the body's normal functioning **Metabolic Health:** This refers to an individual's possession of optimal levels of blood sugar, triglycerides, high-density lipoprotein (HDL) cholesterol, blood pressure, and waist circumference, without using medications

**Metabolic Syndrome:** Metabolic syndrome (MetS) is a cluster of risk factors for type 2 diabetes (T2DM) and cardiovascular disease (CVD). It is defined by five components [raised waist circumference (WC), raised triglycerides, reduced high density lipoprotein (HDL) Cholesterol, raised fasting glucose and raised blood pressure (BP)].

**Motivational interviewing:** "Motivational interviewing is a directive, client-centered counseling style for eliciting behavior change by helping clients to explore and resolve ambivalence"[1]

**Physical activity:** Is defined as "any bodily movement produced by skeletal muscles that results in caloric expenditure"[2].

**Prevalence of metabolic health:** This refers to the proportion of people who have optimal levels of all the risk factor variables without any medication.

**Reproductive age:** This refers to the female in the age group 15-49 years.

**Reproductive factors:** This refers to factors of reproductive history including early menarche, parity, miscarriages, and menopause.

**Risk factor:** This refers to an 'aspect of personal behavior or lifestyle, an environmental exposure, or a hereditary characteristic that is associated with an increase in the occurrence of a particular disease, injury, or other health condition'.

**Modifiable risk factor:** A behavioral risk factor that can be reduced or controlled by intervention, thereby reducing the probability of disease for instance obesity, dietary habits, psychosocial factors, alcohol abuse and cigarette smoking.

**Non-modifiable risk factor:** A risk factor that cannot be reduced or controlled by intervention for instance age, sex, race, genetics/family history

## PROJECT SUMMARY

Metabolic Syndrome (MetS) has seen a significant rise in prevalence worldwide, including regions such as sub-Saharan Africa and low-income countries like Uganda, where females are more affected than males. Despite the availability of effective interventions, the effectiveness of lifestyle modification interventions in low-income countries such as Uganda is not well-established, unlike in high-income countries.

## **General objective**

To evaluate the effect of a 12-week community-based nutrition education, physical activity and motivational interviewing intervention on MetS among females of reproductive age in central Uganda.

## Methods

This design is an individual randomized parallel-group study conducted among 120 participants (intervention (n=60) or control (n=60) groups) aged 15-49 in Wakiso district, central Uganda. The intervention will include an information leaflet, group nutrition education sessions, group physical activity sessions and group motivation interviewing sessions. The control group will receive the usual standard of care and referrals to the nearest health facilities.

Data will be collected at baseline and end line on sociodemographic factors, selected cardiovascular outcomes, biochemical outcomes, anthropometric measures, behavioural outcomes, and knowledge on MetS, using a household survey including a modified STEPS questionnaire.

Analyses will be conducted using Stata (SE/14.0). Descriptive analysis (means and SD) and Chi-square tests for categorical outcomes will compare baseline characteristics and metabolic risk factors between the intervention and the control groups. Student T-tests will be applied to continuous variables to assess cardio-metabolic parameters and their variations. Statistical significance will be at p < 0.05. A multilevel generalized linear mixed model (GLMM) will analyze the impact of time and study group on metabolic outcomes independent of other factors. The study will be conducted for 12 weeks following recruitment of the participants.

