#### **3.7 Sample size Determination**

#### Sample size for participants with Metabolic Syndrome (Primary outcome variable)

Using Power analysis computation of sample size with G.Power 3.1.9.4 software. The estimates will be based on a significance level of 5% and power of 80% to detect a difference between-group of 0.20 in MetS prevalence after 3 months intervention. A sample size of 98 is obtained. After accounting for design effect the sample size is 104. Assuming a dropout rate and failure to consent rate of 10%, 120 participants will be needed in total. 60 participants in the intervention and 60 in the non- intervention groups.

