#### **Randomization: Sequence generation**

The randomization procedure will be automatically performed by a biostatistician to minimize the differences between the two groups for all stratifying variables. Using a computer random number generator a randomisation list of permuted blocks of size 8 with an allocation ratio of 1:1 will be generated. Then the participants will be randomly allocated to either the intervention arm (60) or the control group (60) and followed up for 3 months.

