#### **Randomization: Allocation Concealment**

Random allocation will be conducted with minimization algorithm centrally in a single step to obtain two lists of nominative data. The allocation concealment will be by sealed opaque envelop to preserve allocation concealment. The biostatistician will assign numbers to the envelopes from 1 to 120. This will help prevent the possibility for researchers to predict or influence the allocation of participants. Due to practical reasons, we shall obtain informed consent after the randomization process.

The study coordinator who will be blinded to the randomisation allocation list will enrol the participants. The numbered envelopes will be distributed in sequence from 1 to 120 to a list of names from the baseline survey diagnosed with Metabolic Syndrome. This list of names will be generated after randomisation of those names.

All the individuals belonging to the intervention group will be separated from the individuals belonging to the control group and two allocation lists will be generated with control and intervention groups. The principal investigator will then follow up and identify the study participants in their respective villages, with the assistance of the village chairpersons.

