#### **Data Analysis**

The data for participants who attend less than 60 % of their respective intervention sessions will be excluded from analyses.

Participants with attendance rates below 60% in the intervention sessions will not be included in the analyses.

The analyses will be conducted using Stata statistical software (SE/ 14.0, StataCorp, College Station, TX, USA. Variables will be expressed using descriptive analysis (means and SD). The baseline information for both comparison and intervention groups will be statistically compared regarding all influencing factors at baseline and end line (12 weeks). The chi-square test will analyse for differences in categorical outcomes, including baseline study characteristics, metabolic risk factors (waist circumference (WC), blood pressure (BP), triglycerides, fasting blood sugar(FBS), and high-density lipoprotein (HDL) Cholesterol),

and other factors including dietary habits such as fruits and vegetable intake, and food groups consumed. Behaviours, including smoking, alcohol intake, and physical activity, will also be analysed.

The Student T test for independent samples and variance analysis (ANOVA) will compare cardio-metabolic parameters (and their variations - to find any differences between findings) between the intervention group and the comparison group at the baseline and end of the intervention (after-before).

A 2 factor (2 x 2; group x time) repeated measures analysis of variance (ANOVA) will be performed for each dependent variable and a 1-way ANOVA will be used to assess the significance of differences between groups on the dependent variables assessed. Tukey's post hoc analysis will be performed if there is a significant finding. The T test for paired data will be applied to investigate within –group variable variations (after-before). Statistical significance will be set at p < 0.05.

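### Allocation is said to balance unnamed stratifying variables, but the between-arm tests leave them out, so the primary outcome has no adjusted analysis; if those variables are prognostic, precision is lost

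*Protocol*

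**What the plan says.** **Allocation.** Protocol section 3.7, Randomization: Sequence generation, gives the aim as "to minimize the differences between the two groups for all stratifying variables". The paragraph on allocation concealment then says: "Random allocation will be conducted with minimization algorithm centrally in a single step to obtain two lists of nominative data". Neither paragraph names a variable. The first also specifies a 1:1 computer-generated list in permuted blocks of 8, with no strata. The second hands out envelopes 1 to 120 in order to a randomly ordered list of names.

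**Analysis.** The Project Summary (Methods) says "Student T-tests will be applied to continuous variables to assess cardio-metabolic parameters and their variations", with chi-square tests for categorical outcomes. Data Analysis (section 3.9) repeats this: "The Student T test for independent samples and variance analysis (ANOVA) will compare cardio-metabolic parameters". It adds a chi-square test for categorical outcomes, a group-by-time repeated-measures ANOVA and a one-way ANOVA. None of these has a covariate.

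Data Analysis also plans a multilevel GLMM for blood pressure, waist circumference, HDL-C, fasting glucose and triglycerides. It is adjusted for schooling, age, job and an open-ended remainder.

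**Primary outcome.** Section 3.6 defines it as the between-group change in MetS prevalence at 3 months, which is binary. The detailed GLMM text does not list it.

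**The concern.** When allocation forces the arms to agree on a factor that predicts outcome, chance imbalance in that factor no longer contributes to the true error of the treatment comparison. A t test, chi-square test or ANOVA that omits the factor still counts its variance in the standard error. The interval is then wider than it need be, and the test gives up some of the precision that balancing was meant to buy. An analysis that includes the balancing variables recovers it.

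The primary outcome is the most exposed, because no adjusted analysis is stated for it. The trial has only 120 women, so a few points of power are worth having.

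**Working it through.** **1. The plan's own sample size.** Section 3.7 assumes a "significance level of 5% and power of 80% to detect a difference between-group of 0.20 in MetS prevalence after 3 months intervention". It then says "A sample size of 98 is obtained", "After accounting for design effect the sample size is 104" and "Assuming a dropout rate and failure to consent rate of 10%, 120 participants will be needed in total". The control rate and sidedness are not given. With two-sided 5%, no continuity correction and assumed rates of 0.95 and 0.75 (mean 0.85):

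- n per arm = [1.960·√(2·0.85·0.15) + 0.842·√(0.95·0.05 + 0.75·0.25)]² / 0.20² = (0.990 + 0.408)² / 0.04 = 48.8, so 49 per arm and 98 in total.

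One-sided 5% with 0.90 and 0.70 also gives 98, so the figure can be matched but not derived from the text alone. Next, 104/98 = 1.061 is the implied design effect. Then 104/0.90 = 115.6, so 116; 120 leaves room for 13.3% loss (1 − 104/120). No step mentions covariate adjustment, so the planned 80% is for an unadjusted test.

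**2. Direction, in closed form.** Let the balanced variables explain a share R² of the variance of the quantity tested, with exact balance. The unadjusted standard error is too large by 1/√(1 − R²), and the true two-sided type I error is 2·[1 − Φ(1.96/√(1 − R²))].

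| R² (assumed) | SE inflation | Type I error |
|---|---|---|
| 0.1 | 1.054 | 0.039 |
| 0.2 | 1.118 | 0.028 |
| 0.3 | 1.195 | 0.019 |

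**3. Continuous outcome, simulated.** Minimisation on three assumed binary factors, biased-coin probability 0.8, n = 120, standardised effect held at 0.515, 2,500 runs per cell. The comparison is a t test against a linear model with the three factors.

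| R² | Type I: unadjusted / adjusted | Power: unadjusted / adjusted |
|---|---|---|
| 0 | 0.053 / 0.050 | 0.82 / 0.82 |
| 0.1 | 0.042 / 0.054 | 0.81 / 0.85 |
| 0.2 | 0.033 / 0.048 | 0.82 / 0.88 |
| 0.3 | 0.020 / 0.053 | 0.85 / 0.91 |

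Simulation error is about 0.004 on a type I error of 0.05 and 0.007 on a power of 0.85. Adjustment gains about 4 to 7 points, and unadjusted power stays above 0.80.

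**4. Binary MetS, simulated.** Same minimisation, n = 104. Type I error is at 0.85 in both arms; power is at 0.95 against 0.75. The comparison is a chi-square test against a linear model for the binary outcome with the three factors.

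| Odds ratio per factor | Type I: unadjusted / adjusted | Power: unadjusted / adjusted |
|---|---|---|
| 1 | 0.041 / 0.042 | 0.84 / 0.84 |
| 2.7 | 0.045 / 0.051 | 0.86 / 0.87 |
| 5 | 0.034 / 0.047 | 0.86 / 0.89 |
| 11 | 0.030 / 0.049 | 0.88 / 0.92 |

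The gain is about 1 to 5 points, and the upper end needs very strong factors.

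**5. The opposing effect of delivery groups.** Section 3.1 has the intervention delivered in 5 groups of 12. The t test, chi-square test and ANOVA ignore this. Applying the protocol's own design effect to the whole comparison, the type I error of a nominal 5% test becomes 2·[1 − Φ(1.96/√1.061)] = 2·[1 − Φ(1.903)] = 0.057. As a rough sum, true variance relative to nominal is (1 − R²) + 0.061, so the two effects cancel near R² = 0.06.

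**The case against.** **The premise is not settled.** The block list with sequential envelopes balances no covariate. Under it, the unadjusted tests are not conservative for this reason. This stands: the loss depends on the minimisation text being what is done, and the allocation text must be reconciled first. It does not remove the point, since the protocol states balance on stratifying variables as its aim and names minimisation as the method.

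**The GLMM may already cover it.** The Project Summary applies the model to metabolic outcomes in general, and its open covariate list might take in the balancing variables. An exact covariate list can be left to an SAP. But the detailed text confines the model to five components and does not link its covariates to the allocation. The protocol itself fixes the unadjusted tests. The chi-square paragraph does not name MetS; it is simply the only stated test that fits a binary endpoint.

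**Stronger readings that a reader might infer.**

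- *The p-values are too conservative and the true type I error is below 5%.* This needs prognostic factors and real balance, and neither is documented. Ignoring the delivery groups pushes the error upward.
- *Power falls to 77%, 73% or 68% at R² of 0.1, 0.2 or 0.3.* Those values come from Φ(2.80 − 1.96/√(1 − R²)), which sets the adjusted analysis at 80% and so shrinks the effect as R² grows. The protocol's 80% assumes no adjustment. With the effect held fixed, unadjusted power is 0.81 to 0.85.

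**R² may be small.** Several planned tests use after-minus-before changes, from which stable baseline factors may largely cancel. This stands: R² must refer to the quantity tested.

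**Conclusion.** The point holds conditionally. The protocol claims balance on stratifying variables, omits them from its between-arm tests, and states no adjusted analysis for the primary outcome. If the allocation does balance these variables and they are prognostic, the unadjusted tests are less precise than an adjusted analysis and, from that source alone, conservative. Type I error is then about 0.04 to 0.02 for a continuous outcome over the assumed range. The power cost is the 4 to 7 points (continuous) or 1 to 5 points (binary) shown in the working. With non-prognostic factors there is no cost.

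All factor strengths are assumptions, because the protocol names no factor. The simulations also analyse everyone allocated, whereas the protocol seeks consent after randomisation and drops low attenders, which could erode the balance. Neither a shortfall against the planned 80% nor net conservatism of the tests is established. This is an improvement that should be made, not a fault that invalidates the trial.

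**What to change.** - **Section 3.7, both randomisation paragraphs:** state one allocation method and name the variables it balances. Until that is done, the covariates cannot be specified.
- **Data Analysis, primary outcome:** analyse MetS at 3 months with a logistic or binomial model containing those variables, reported as a standardised risk difference with 95% CI.
- **Data Analysis, continuous outcomes:** use linear models, or the planned GLMM, with the same variables named explicitly, in place of the plain t test or one-way ANOVA for between-arm comparisons. Align the Project Summary.

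The cost is analysis wording and a few degrees of freedom. If the variables prove unrelated to outcome, adjusting loses essentially nothing. If unstratified blocks are what is finally used, this particular argument falls away and the text should drop its references to stratifying variables and minimisation.

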## Ethics and dissemination

The study received ethical approval from the Higher Degrees, Research, and Ethics Committee of Makerere University School of Public Health and from the Uganda National Council for Science and Technology.

The results of the study will be disseminated through peer-reviewed publications and scientific meetings.

#### **1.0 INTRODUCTION/ BACKGROUND**

#### 1.1 Background

Metabolic Syndrome (MetS) is defined by a clustering of risk factors for cardiovascular disease (CVD) and type 2 diabetes mellitus (T2DM). The risk factors consists of five components [raised waist circumference (WC), raised triglycerides(TG), reduced high density lipoprotein (HDL) Cholesterol, raised fasting glucose and raised blood pressure(BP)[3], that occur together more often than by chance alone [3].

Globally, metabolic syndrome (MetS) is a problem of public health concern (K. Alberti et al., 2009; Kaur, 2014). Prevalence of MetS ranges from < 10% to 84% [4, 5], In Africa it ranges between 0-50% [6-8]. In Uganda, studies on the prevalence of MetS in the general population are currently lacking However, a study conducted among HIV individuals on first line antiretroviral therapy in south Western Uganda revealed a high MetS prevalence of (58%)[9], while one among patients with severe mental illness in a regional tertiary hospital in western Uganda indicated a prevalence of 23.5%. The consequences of MetS include an increased risk for type II diabetes mellitus, cardiovascular diseases and stroke[10, 11] and their associated morbidity and mortality. It is noteworthy, that the prevalence of MetS in most populations is higher in females as compared to males [9, 12-14]. Additionally, the effects of MetS in females of reproductive age and their off springs leading to poor maternal health, obstetric and perinatal outcomes[15, 16] and contribute to pregnancy induced hypertension, pre-eclampsia, gestational diabetes and infertility as well as prematurity, abortions, macrosomia and neural tube defects may occur. However, the prevalence of MetS in the female population in Uganda and its associated factors is currently unknown.

Currently, the Ministry of Health has carried out some interventions to control cardiovascular diseases in general, with attention focused largely on identification of individual risk factors for CVDs like hypertension and diabetes. However, there are limited interventions for Metabolic Syndrome. Probably due to a paucity of research on effective interventions and lack of guidelines for management of Metabolic Syndrome. Nutrition education and counselling interventions are known to influence dietary and lifestyle behavioral change. Lifestyle/dietary change is essential in the prevention and management of MetaS. Nutrition promotion and lifestyle modification interventions including nutrition education and counselling interventions have been effectively used to address MetS or its components in other settings [17-21]. However, the effectiveness of such interventions among women of

reproductive age in Uganda have little been studied. Thus there is limited information on effectiveness of such interventions in Uganda..

Thus, there are gaps on an effective community nutrition education intervention that can promote dietary/lifestyle behavioral change for management of MetS among females of reproductive age in Uganda.

This research will therefore investigate the effect of a nutrition education and physical activity intervention among females of reproductive age with MetS in Central Uganda in order to contribute to inform the design of appropriate interventions for management of MetS in Uganda.

#### **1.2 RATIONALE FOR PROPOSED TRIAL**

This study will determine the effect of a nutrition education, physical activity and motivation interviewing on metabolic syndrome indicators (WC, BP, HDL, TGS, blood sugar). Women in Uganda generally are instrumental in making key decisions in food selection (buying), processing and preparation for their families, it is necessary to provide them with essential education/knowledge to make appropriate decisions to prepare and provide food which is healthy, nutritious and adequate, in addition to encouraging them to adopt physical activity. These lifestyles changes may help women with MetS and their families to have improved outcomes. The intervention will therefore be designed to educate women with MetS on how to effectively utilize locally available foods and adopt physical activity in order to improve their metabolic profile.

The primary objective of the study is to assess the effect of interventions for preventing and managing Metabolic Syndrome, for informing policy.

#### 2.0 OBJECTIVES

#### 2.1 GENERAL OBJECTIVE

The overall objective of the trial is to determine the effect of a community-based group nutrition education, physical activity, and group motivational interviewing intervention regarding dietary intake and physical activity on Metabolic Syndrome among females of reproductive age in Wakiso district, Central Uganda.

## **2.2 SPECIFIC OBJECTIVES 2.2.1 Primary objective**

The primary objectives of the trial are as follows:

 To determine the effect of nutrition education, physical activity and motivational interviewing intervention on Metabolic Syndrome among females aged 15-49 years in Wakiso district.

#### 2.2.2 Secondary objective

• To determine the effect of nutrition education, physical activity and motivational interviewing intervention on metabolic syndrome outcomes (blood pressure, high-density lipoprotein cholesterol, triglycerides, fasting blood sugar, waist circumference) and dietary intake, physical activity among females aged 15-49 years with metabolic syndrome in Wakiso district.

